4.1 Registration and Randomization

Eligible patients will be entered on study at UCSF by the Study Coordinators. All patients who sign the informed consent document will be registered in OnCore and the Brain Tumor Research Center Tissue Bank database.

Arm 1: Patients will receive IMA950- poly-ICLC vaccine plus varlilumab. **Arm 2**: Patients will receive IMA950- poly-ICLC vaccine alone.

The study is designed with a staggered safety lead-in with the first 3 patients assigned to Arm 2. The first 3 patients of the study will be enrolled in Arm 2 in a staggered manner as follows. After the first patient of the study is enrolled in Arm 2, Patient number 2 and 3 will not be enrolled until the previous patient receives 4 pre-surgery vaccines and recover from clinically indicated surgery for at least 6 weeks after surgery without a regimen-limiting toxicity (RLT) to confirm the safety of IMA950-poly-ICLC vaccine.

If any of the first 3 patients on Arm 2 shows a RLT (see definition in section 5.3), an additional 3 patients (patients 4, 5 and 6) will be enrolled in the same, staggered manner in Arm 2 while Arm 1 enrollment is held. If 2 or more of the patients on Arm 2 show a RLT, the arm will be considered intolerable and the study will be closed. If only one total of the 6 patients shows an RLT in Arm 2, the randomized design will be cancelled and the study will proceed with Arm 2 only to primarily evaluate the safety of the Arm 2 regimen. When the study is completed with the total evaluable 15 patients in Arm 2, we will review the safety data, and discuss with the FDA and IRB regarding the extension of the study to Arm 1.

If none of the first 3 patients treated on Arm 2 demonstrates a RLT, then 3 further patients will be enrolled in Arm 1 (with varlilumab) in the same staggered manner (subsequent patients will not be enrolled until the respective previous patient receives 4 pre-surgery vaccines and recover from clinically indicated surgery for at least 6 weeks after surgery without an RLT to confirm the safety of IMA950-poly-ICLC-varli treatment. If one of first 3 patients on Arm 1 shows a **Regimen Limiting Toxicity** an additional 3 patients will be enrolled in the same, staggered manner in Arm 1. If 2 or more of the patients on Arm 1 show a RLT, the arm will be considered intolerable.

12 April 2020 Page 27 of 88 confidential

If Arm 2 is tolerable but Arm 1 is not, then, the study will be carried out with Arm 2 only.

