If both arms are found tolerable, then subsequent patients will then be randomized into one of the two arms for the pre-surgical part of the study. **Arm 1**: Patients will receive IMA950-poly-ICLC vaccine plus varlilumab. **Arm 2**: Patients will receive IMA950-poly-ICLC vaccine alone. The randomization will take place in a 1:1 ratio between the two arms with the stratification based on whether the patient is newly diagnosed vs. recurrent.

Patients will be assigned to treatment by means of the UCSF Biostatistics Facility randomization system in an open label fashion. Information on the two arms will be loaded into the database and the treatment arm assigned to the subjects when the subject's initials and ID# are entered into the program. Results of randomization will not be blinded, and no placebo will be used.

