4.3 Replacement

Patients who receive at least 4 post-surgery vaccines will not be replaced because their PBMC on week 13 would allow for the primary endpoint evaluation. Subjects who are considered non-evaluable for the immunological endpoint will be replaced but still evaluated for the primary endpoint of safety and the secondary endpoint of efficacy. Evaluable patients for the immunological primary endpoint are study-eligible patients who receive at least four post-surgery vaccines. If the pathological diagnosis upon the resected tissue indicates WHO III or IV grade tumors, those patients will be ineligible for post-surgery courses and replaced.

5 Treatment Plan

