8.1 Immunological Monitoring of PBMCs

Analyses of immune responses in PBMC will allow non-invasive evaluation of vaccine-induced immune response. As one of two co-primary endpoints of the current study, we will determine the response rate and magnitude of CD4+ and CD8+ T-cell responses against the IMA950 peptides in pre- and post-vaccine PBMC using a novel, flow-cytometry-based 2D *ex vivo* assay system. We will determine whether Arm 1 patients demonstrate higher response rate and/or magnitude of response compared with Arm 2 patients.

As the primary method of PBMC analysis, we will use a novel 2D multimer staining-based assays. ⁸³ The use of fluorescently labeled MHC multimers has become an essential technique for analyzing disease- and therapy-induced T-cell immunity. However, limitations on available PBMCs from patients preclude a comprehensive analysis of T-cell immunity. To address this issue, Hadrup et al. developed a combinatorial encoding strategy that allows the parallel detection of a multitude of different T-cell populations in a single sample (2D multimer staining-based assays). ⁸³ Detection of T-cells from PBMC by combinatorial encoding is as efficient as detection with conventionally labeled multimers but results in a substantially increased sensitivity and, most notably, allows comprehensive screens to be performed. We have confirmed that we can detect increases of IMA950-specific T-cells using PBMC samples obtained from GBM patients receiving IMA950 vaccines.

As the primary method to evaluate the relative immune response levels between two Arms, the relative magnitude of responses against each of IMA950 antigens will be compared between two Arms by comparing the sum of post-vaccine tetramer+ percentages of all time points from all patients in each of two Arms.

As an exploratory evaluation, a subject will be considered to be an immunological responder, if at any of two consecutive post-vaccine time points (i.e., Weeks A13, 19 and A25):

- 1. Presence of a CD4+ or CD8+ T cell population which shows positive tetramer staining against any of IMA950 antigens.
- 2. Four-fold increase of the frequency of the tetramer positive cells within the CD4+ or CD8+ T cell population at the considered post-vaccination time points versus the prevaccination time point.

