12.1 Statistical Analysis Plan

- **12.1.1 Primary Safety Objective:** Evaluate the incidence and severity of adverse events associated with the treatment regime. The proportion of patients experiencing Regimen Limiting Toxicity (RLT, Section 5.3.1) in each arm will be tabulated with 95% exact (Clopper-Pearson) confidence intervals. The proportions of patients experiencing RLT will be compared between arms by the Fisher's exact test. The power of this test is described in Section 12.3. The early stopping rule for RLT is described in Section 12.2.
- **12.1.2 Primary Immunogenicity Objective:** Detection of vaccine-induced immune response in pre- and post-vaccine PBMC. The standardized difference between pre- and post-vaccine PBMC will be compared between arms via a two-sample Student's *t* test. We assume the magnitude of difference will be greater in Arm 1 than Arm 2. If the *t* test assumptions are not met and the data cannot be transformed in such a way that the assumptions are met, a Wilcoxon Rank Sum test will be used. Based on a one-sided two-sample equal variance t-test, the statistical power will be 80% with 15 patients per arm if the difference between arms is at least 0.8 with a standard deviation for both arms of 1.0 with a significance level of 0.10.
- **12.1.3 Exploratory Efficacy Objective:** Evaluation of IMA950-reactive T-cell infiltration and CXCL9/10 expression in tumors resected from Arm 1 and Arm 2 patients. In surgically resected tumor tissues from Arm 1 (IMA950+poly-ICLC and varlilumab) and Arm 2 (IMA950+poly-ICLC alone) patients, we will evaluate numbers of tumor-

12 April 2020 Page 75 of 88 confidential

- infiltrating CD4⁺ T-cells CD8⁺ T-cells (by flow-cytometry) and CXCL10 expression (by RT-PCR). This comparison will be made via two-sample t-tests unless the assumptions are not met then a Wilcoxon alternative will be employed.
- 12.1.4 Exploratory Efficacy Objective: To evaluate IMA950-reactive TCR clonotypes in tumors resected from Arm 1 and Arm 2 patients. Our expectation is to see a higher number of copies of vaccine-specific TCRs (frequency/total tumor DNA) in Arm 1 samples than in Arm 2 samples. This comparison will be made via two-sample t-tests unless the assumptions are not met then a Wilcoxon alternative will be employed.

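### The 80% power in 12.1.2 is right for 15 vs 15, but those 15 appear to include lead-in patients placed by order of entry; no randomised-only supporting comparison is planned

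*Combined protocol and SAP*

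**What the plan says.** Section 12.1.2 compares the pre- to post-vaccine change between arms with a two-sample t test. It is one-sided at 0.10 with an SD of 1.0 in both arms, and "the statistical power will be 80% with 15 patients per arm if the difference between arms is at least 0.8". The lead-in is not mentioned there.

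Section 4.1 describes how patients reach the arms:
- "The study is designed with a staggered safety lead-in with the first 3 patients assigned to Arm 2".
- "If none of the first 3 patients treated on Arm 2 demonstrates a RLT, then 3 further patients will be enrolled in Arm 1".
- If one of those three has a regimen limiting toxicity (RLT), "an additional 3 patients will be enrolled in the same, staggered manner in Arm 1".
- "If both arms are found tolerable, then subsequent patients will then be randomized into one of the two arms", in a 1:1 ratio, "with the stratification based on whether the patient is newly diagnosed vs. recurrent". Assignment is open label.

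Three places bear on who enters the immunological comparison:
- Section 4.3: "Evaluable patients for the immunological primary endpoint are study-eligible patients who receive at least four post-surgery vaccines". Having been randomised is not a condition.
- Section 8.1 describes the arm comparison as "comparing the sum of post-vaccine tetramer+ percentages of all time points from all patients in each of two Arms".
- Section 4.1, in the branch where only Arm 2 continues, uses 15 as the arm's evaluable total, although that branch opens with lead-in patients.

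**The concern.** On the pooled reading, a comparison presented as randomised contains patients whose arm was fixed by when they entered. For them, arm is tied to calendar time and is known before enrolment, and stratification does not protect them. The change from each patient's own baseline may cancel part of any laboratory drift. It does not cancel a difference in case mix.

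The stratification factor that the lead-in bypasses may matter for response. Section 2.7 reports significantly higher IFN-γ responses in Cohort 1 (newly diagnosed) than in Cohort 3, a label I read as the recurrent-disease study. Robust responses were seen in 10 of 13 and 4 of 10 enrolled patients respectively.

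Two things are at stake: how far an arm difference can be called randomised, and whether the choice between a pooled and a randomised-only result is made before the data are seen.

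**Working it through.** **Inputs.** From 12.1.2: difference 0.8, SD 1.0, one-sided 0.10, 15 per arm. From 4.1: lead-in of 3 in Arm 2 and 3 in Arm 1, plus 3 more in Arm 1 after one RLT.

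**Formula.** Power = P(T > t(0.90, df)), where T is noncentral t, df = n1 + n2 − 2, and noncentrality = 0.8 / √(1/n1 + 1/n2).

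**The plan's figure.** For 15 vs 15: df 28, critical value 1.313, noncentrality 0.8 × √7.5 = 2.191, power 81.0%. The stated 80% reproduces.

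**Randomised counts if lead-in patients fill part of the 15.**
- No expansion: 15 − 3 = 12 in each arm. Non-randomised share 6/30 = 20%.
- Expansion, RLT patient not evaluable: 6 − 1 = 5 lead-in patients in Arm 1, so 10 vs 12. Share 8/30 = 27%. Section 5.6.1 takes a patient with an RLT off study. An RLT within 6 weeks of surgery comes before the fourth post-surgery vaccine, which falls 9 weeks after week A1.
- Expansion, RLT late enough that the patient is already evaluable: 15 − 6 = 9, so 9 vs 12. Share 9/30 = 30%.

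| Comparison | Noncentrality | Power | Difference detectable with 80% power |
|---|---|---|---|
| 15 vs 15, pooled | 2.191 | 81.0% | 0.79 SD |
| 12 vs 12, randomised | 1.960 | 73.9% | 0.88 SD |
| 10 vs 12, randomised | 1.868 | 70.8% | 0.93 SD |
| 9 vs 12, randomised | 1.814 | 68.9% | 0.96 SD |

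The randomised rows without expansion and with 10 vs 12 assume that every lead-in patient without an RLT is evaluable. If some are not and randomised patients replace them, power lies between those rows and 81%.

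**How often expansion occurs.** With Section 12.2's expected RLT probability of 1/20, one RLT in the first three and none in the next three, given that randomisation is reached: q = 3 × 0.05 × 0.95² = 0.135 relative to no RLT in the first three. In the expanded route the second three must also be clear, so the ratio is 0.135 × 0.95³ × (1/0.95³) = 0.135, and 0.135/1.135 = 12%.

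**Adjusting the pooled test for newly diagnosed versus recurrent.** Noncentrality = 0.8 × √Σ[n1k·n2k/(n1k + n2k)] over the two strata, df = 30 − 3 = 27, with no credit for reduced residual variance.
- Strata 8 vs 8 and 7 vs 7: sum 7.5, power 80.9%.
- Newly diagnosed 9 of 15 vs 6 of 15: sum 2 × 54/15 = 7.2, power 79.7%.
- 10 of 15 vs 5 of 15: sum 2 × 50/15 = 6.67, power 77.4%.

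The 9 vs 6 case is what three newly diagnosed lead-in patients in one arm and three recurrent in the other would produce on top of a 6 vs 6 randomised split.

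**Sensitivity to bias (assumed; the documents give no value).** If the lead-in groups differ by δ for reasons other than treatment, the pooled difference moves by (3/15)δ. With δ = 0.5 SD the shift is 0.10 SD, and simulation puts the one-sided error at about 15% or 6%, depending on direction. With δ = 1.0 SD it is about 21% to 22%, or 3%. Nominal is 10%.

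**The case against.** No stated figure is wrong. A reader might infer that 12.1.2 overstates its power or that the trial is underpowered. The documents do not support that: 74% and 69% to 71% are powers of a test the plan does not propose.

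Pooling is inferred. The sum in Section 8.1 is a different statistic from the t test in 12.1.2, and Section 4.1's total of 15 belongs to the branch where randomisation is cancelled. The stopping table in 12.2 runs from 3 to 15 patients per arm, but it is a safety rule and does not define the immunogenicity set. The accrual-goal entry in the synopsis, as readable here, shows no total, so a clearer statement may exist in the original layout. This limits the point to the conditional form used here. If 15 per arm are randomised on top of the lead-in, only a request for clarity is left.

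The evidence for bias is thin. Section 2.7 concerns other peptides, a different adjuvant formulation and ELISPOT, and nothing suggests that the lead-in groups will differ in diagnosis.

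Dropping lead-in patients also has a price. The variance of the difference is 2/15 pooled and 2/12 randomised-only. Pooling has the lower mean squared error unless (0.2δ)² exceeds 2/12 − 2/15 = 0.0333, that is, unless δ is above about 0.91 SD. This objection stands. It rules out making the randomised-only test the sole basis for claims, which a reader might otherwise infer. It does not remove the case for having that test as a check, because adjustment for diagnosis cannot correct for entry order or unmeasured case mix.

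**Conclusion.** The concern holds as a gap in the analysis plan, not as an error in the power statement. On the natural but unstated reading, 20% of the primary immunological comparison is non-randomised (27% to 30% after expansion), and 12.1.2 plans neither a randomised-only check nor adjustment for the stratification factor. The randomised patients alone have about 74% power, or about 69% to 71% after expansion, against 81% pooled.

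This rests on three assumptions: lead-in patients count towards the 15, those without an RLT are evaluable, and the effect and SD in 12.1.2 apply. The 12% expansion frequency also depends on an RLT probability taken from earlier vaccine studies that, as Section 2.7 describes them, did not include varlilumab. Whether any bias exists, and in which direction, cannot be known from the documents.

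**What to change.** In 12.1.2:
1. State whether lead-in patients count towards the 15 per arm. If 15 per arm are randomised in addition to the lead-in, say so; the 80% then stands for the randomised test.
2. If they are pooled, keep the pooled test as primary and pre-specify a randomised-only between-arm comparison as a supporting (sensitivity) analysis. State its power: about 74% at 12 vs 12, and about 69% to 71% after Arm 1 expansion (9 or 10 vs 12).
3. Adjust the pooled test for newly diagnosed versus recurrent. Power stays at about 77% to 81% for the imbalances checked; a larger imbalance would cost more.
4. Commit to reporting any disagreement between the pooled and randomised-only results as a limit on the randomised claim.

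The cost is a few sentences, one extra analysis and a less favourable power figure for the supporting comparison. No patients or samples are added, and the safety lead-in is unchanged.

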9.2.3 Overall Survival (OS) and Progression-Free Survival (PFS)

PFS is defined as the duration of time from start of treatment to time of progression or death. Patients who have not yet progressed or died will be censored at the time of their last follow-up.

All patients will be followed for a minimum of 2 years, so that their actual 2-year OS and PFS can be determined. OS is defined as the time from start of treatment to time of death. Patients who have not yet died will be censored at the time of their last follow-up.

Tumor recurrence will be assessed minimally at week A25, and patients will be followed with MRI scans and clinical visits as standard of care. Even though we cannot schedule precise time points for follow-up MRIs (because that portion is not a part of the study), we will obtain 2-year PFS as exploratory data. Since LGGs are infiltrative tumors which typically do not enhance with contrast administration, for evaluation of response and PFS,

12 April 2020 Page 64 of 88 confidential

the tumor (i.e., target lesion) will be measured from the T2 or FLAIR MRI images. In case there is an enhancing lesion at the baseline, careful discussion will be made as to whether the pathology information as WHO grade II tumor truly represents the status of the tumor. If the enhancing tumor is still considered to be grade II, the size of the enhancing lesion will be used for evaluation.

9.2.4 Evaluation of PBMC responses against IMA950 in association with OS, PFS and frequency of IMA950 reactive T-cells in the tumor

We will attempt to determine whether vaccine-reactive T-cells in PBMC: 1) correlate with clinical benefits, such as PFS and OS; 2) correlate with observations in the glioma TME; and 3) is higher in Arm 1 over Arm 2 patients.

9.2.5 To tabulate tumor objective response rate (ORR) (According to LGG RANO if there is measurable tumor after surgery).

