- **12.1.5 Exploratory Efficacy Objective:** To estimate overall survival (OS) and progression-free survival (PFS) in the two arms. Product limit (Kaplan-Meier) estimates of the OS and PFS functions will be calculated with 95% Greenwood confidence regions. The trial is not adequately powered for the log-rank test that compares survival functions between arms.
- **12.1.6 Exploratory Efficacy Objective:** Evaluation of PBMC responses against IMA950 in association with OS, PFS and frequency of IMA950 reactive T-cells in the tumor. The association of the immunological parameter with PFS and OS will be evaluated using proportional hazards (Cox) regression. Frequencies will be tabulated.
- **12.1.7 Exploratory Efficacy Objective:** Tabulate tumor objective response rate (ORR). The (multinomial) distributions of responses in patients with measurable tumors (Section 9.2.3) will be calculated with simultaneous (Sison & Glaz) confidence regions. The trial is not adequately powered for a comparison between arms using Fisher's exact test.
- **12.1.8 Exploratory Efficacy Objective:** Evaluation of leukocyte phenotypes in PBMC samples. Frequencies will be tabulated to compare the distributions of the phenotypes between arms.
- **12.1.9 Exploratory Efficacy Objective**: Evaluation of pharmacokinetics for varlilumab. The purpose of this exploratory efficacy objective is to capture minimum and maximum values for the different pharmacokinetics measures. The purpose is not testing hypothesis; therefore descriptive statistics will be reported.

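### Greenwood regions give a zero-width (or undefined) 95% interval for 2-year OS in any arm with no deaths; with about 15 patients per arm, an exact interval should be specified

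*Combined protocol and SAP*

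**What the plan says.** Section 12.1.5 sets the method for both time-to-event endpoints: "Product limit (Kaplan-Meier) estimates of the OS and PFS functions will be calculated with 95% Greenwood confidence regions". It names no transformation (plain, log or log-log) and says nothing about an arm without events. It also says that the trial is too small for a log-rank comparison.

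Section 9.2.3 makes survival at 2 years a quantity of interest: "All patients will be followed for a minimum of 2 years, so that their actual 2-year OS and PFS can be determined". It defines the time axis: "OS is defined as the time from start of treatment to time of death".

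The arm size comes from the immunogenicity endpoint in Section 12.1.2, where the plan states that "the statistical power will be 80% with 15 patients per arm if the difference between arms is at least 0.8". That calculation uses a one-sided t test, an SD of 1.0 in each arm and alpha 0.10. After the safety lead-in, Section 4.1 says: "The randomization will take place in a 1:1 ratio between the two arms".

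Two other statements matter. Section 4.3 says that patients not evaluable for the immunological endpoint "will be replaced but still evaluated for the primary endpoint of safety and the secondary endpoint of efficacy", so the OS set may be larger than 15 per arm. Section 12.1.1 already uses exact Clopper-Pearson intervals for the proportion with regimen-limiting toxicity in the same small arms.

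**The concern.** Greenwood's formula sums a term for each event time. Before the first event the sum is empty, so the variance is zero and the region has no width. For a 2-year OS figure in a small arm of grade II glioma patients this can be the final answer and not only a feature of the early part of the curve. If nobody in the arm has died by 2 years, the stated method prints a 95% interval of 100%-100%, or nothing at all on the log-log scale.

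Fifteen survivors out of 15 do not establish 100% survival. Because no survival test is planned between the arms, these regions are the only statement of uncertainty that Section 12.1.5 offers for OS. A reader of the results could take a zero-width interval as certainty, or could be left without an interval.

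**Working it through.** **Inputs from the documents.** 15 patients per arm (12.1.2); Kaplan-Meier with 95% Greenwood regions (12.1.5); at least 2 years of follow-up for all (9.2.3).

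**Input not in the documents.** True 2-year OS, S. The background says only that these tumours recur and lead to death in most patients, without a time frame, and Section 2.7 gives PFS medians only. I assume S = 0.90, 0.95 and 0.98, and look below that range as a check.

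**Step 1: the plan's own figure.** Power of a one-sided two-sample t test with n = 15 per arm, difference 0.8, SD 1.0 and alpha 0.10: the noncentrality is 0.8 / sqrt(2/15) = 2.19 on 28 degrees of freedom, and power is 0.81. The stated 80% is reproduced, so 15 per arm is the right design size to use.

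**Step 2: the interval with no deaths.** With complete follow-up to 2 years, the Kaplan-Meier estimate is the proportion alive, p = 1 - d/n, where d is the number of deaths, and the Greenwood variance is p(1 - p)/n. For d = 0, p = 1 and the variance is 0.
- Plain: 1 ± 1.96 × 0 = 100%-100%.
- Log-log: needs log(-log 1), which is undefined.
- Clopper-Pearson for 15 of 15: the lower limit is 0.025^(1/15) = 0.782, so 78%-100%.

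This step needs no assumption about survival.

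**Step 3: how often.** P(no deaths in an arm) = S^n, and P(at least one of two arms has none) = 1 - (1 - S^n)^2.

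| Assumed 2-year OS | No deaths, n = 15 | At least one of two arms with none, n = 15 |
|---|---|---|
| 0.90 | 21% | 37% |
| 0.95 | 46% | 71% |
| 0.98 | 74% | 93% |

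A single arm passes 50% only if S is at least 0.5^(1/15) = 0.955.

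**Step 4: coverage.** Sum the binomial probabilities of the death counts whose interval contains S, taking the zero-death Greenwood interval as the single point 100%.

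| Assumed 2-year OS | Plain Greenwood, n = 15 | Log-log, n = 15 | Plain Greenwood, n = 20 | Clopper-Pearson, n = 15 |
|---|---|---|---|---|
| 0.90 | 79% | 74% | 88% | 98.7% |
| 0.95 | 54% | 50% | 64% | 99.5% |
| 0.98 | 26% | 23% | 33% | 99.7% |

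The n = 20 column allows for replaced patients who stay in the efficacy evaluation. A Kaplan-Meier simulation with n = 15 and 10% loss by 24 months gives 77% / 52% / 25% for plain Greenwood, so modest censoring changes little.

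**Step 5: where the shortfall comes from.** Given at least one death, plain Greenwood coverage over the same range is 99.7%-99.9%. At S = 0.90, for example, 0.792 / (1 - 0.206) = 0.997. The low overall figures are therefore close to 1 - S^15.

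**Step 6: below the assumed range, n = 15.** At S = 0.85 an arm has no deaths 9% of the time, and plain coverage is 90%. At S = 0.80 these are 4% and 81.5%. There the one-death interval also misses, because its lower limit is 80.7%, so Step 5 does not extend that far.

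**Step 7: PFS.** Assuming exponential times with the earlier studies' medians of 17 and 12 months, 2-year PFS is 0.5^(24/17) = 0.376 and 0.5^(24/12) = 0.25. The chance of no event in 15 patients is 0.376^15, about 4 in 10 million, or less.

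**The case against.** The strongest reply is that OS is exploratory in a pilot trial, no decision depends on it, and an interval printed as 100%-100% is so plainly degenerate that few readers would trust it. That stands, and it limits the importance of the point. It does not make the stated method correct.

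Several stronger readings are tempting, and the documents do not support them.

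- A reader might infer that an arm without deaths is likely, or that 26%-79% coverage follows from the plan. Both need a 2-year OS that the documents never give. At 0.90 the chance is only 21%. Recurrent and previously treated patients are eligible, and the OS set may exceed 15; a larger set makes zero deaths less likely.
- A reader might infer that Greenwood intervals are too narrow in general here. Over the assumed range they are not once a death has occurred (Step 5). With one death in 15, the log-log interval of 61%-99.0% is wider than the exact 68%-99.8%.
- A reader might infer that arms with 0 and 1 deaths would look sharply separated. With plain Greenwood the one-death interval is 80.7%-106%, truncated at 100%, so it includes the other arm's 100%. Only the log-log version stops short, at 99.0%, and the plan does not choose that scale.
- A reader might extend the point to PFS. Nothing computed supports that (Step 7).

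It is also fair to say that Section 12.1.5 attaches the regions to the survival functions and does not mention a 2-year interval by name. However, Section 9.2.3 singles out 2-year OS, and the region at 2 years is the only interval the plan supplies for it.

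**Conclusion.** The point holds in a limited form. For any arm with no deaths by 2 years, the planned method gives a zero-width or undefined 95% interval, where 15 of 15 alive supports only 78%-100%. That is wrong as written and rests on no survival assumption. Its frequency does rest on one: 21% / 46% / 74% per arm of 15 if true 2-year OS is 0.90 / 0.95 / 0.98, with plain Greenwood coverage of 79% / 54% / 26%, or 88% / 64% / 33% with 20 per arm. Over that range nearly all the loss comes from the zero-death case. Because OS is exploratory and descriptive, this is a minor correction.

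**What to change.** In Section 12.1.5, add a rule that 2-year OS in each arm will be reported with a 95% exact (Clopper-Pearson) interval where vital status at 2 years is complete, or with a beta-product interval if any patient is censored earlier, and that no Greenwood interval will be reported for an arm without deaths. An OS curve for an arm with deaths, and the PFS curves, can keep Greenwood regions.

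The cost is one sentence and no new data. The exact method is already in the plan for regimen-limiting toxicity. The OS intervals become wider and somewhat conservative: coverage is 98.7%-99.7% over the assumed range, against a nominal 95%. The rule should be fixed before the survival data are analysed, so that the choice cannot appear to depend on the number of deaths.
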